1.4 Exploratory Objectives

- 1.4.1 To assess the frequencies of non-transmitted epitope escape mutants prior to ART initiation and after 48 weeks of ART **on Step 1 by sequencing HIV variants, including single genome sequencing and next generation (deep) sequencing.**
- 1.4.2 To investigate CAHD in CD4+ T-cells and across subsets (e.g., naïve, central memory, effector memory), single copy HIV-1 RNA, and HIV-1-specific immune responses in blood; CAHD in gut; and CAHD and single copy HIV-1 RNA in cerebrospinal fluid (CSF) at any time **on Step 1** from week 60 to week 72 in participants who **consent and** undergo the optional procedures and have available data.
- 1.4.3 To characterize the effects of early ART on innate immune responses during and after AHI, including natural killer cell subset frequencies, phenotype, and function prior to ART initiation and while HIV-1 RNA is suppressed on ART.
- 1.4.4 In participants with detectable CAHD at any time point prior to ART initiation and while HIV-1 RNA is suppressed on ART, to quantify episomal HIV-1 DNA by qPCR for 2-LTR circles and derive the quantity of integrated HIV-1 DNA from the total and unintegrated DNA (unintegrated linear DNA or 1-LTR circles would have a negligible contribution after 48 weeks of therapy **on Step 1**).
- 1.4.5 To investigate the relationship between genetic factors (human leukocyte antigen [HLA] typing and CCR5 delta-32 genotyping) and virologic and immunologic outcomes prior to ART initiation and while HIV-1 RNA is suppressed on ART.
- 1.4.6 To investigate integration sites prior to ART initiation and while HIV-1 RNA is suppressed on ART.
- 1.4.7 **To store samples for future evaluations of HIV-1 reservoirs with novel assays, HIV-specific immune responses, viral sequencing, and genetic factors.**
- 1.4.8 **To characterize the immunologic, virologic, and clinical characteristics of AHI, including response to ART.**
- 1.4.9 **To evaluate the performance of HIV diagnostic assays during AHI, including testing algorithms to distinguish between acute infection, chronic infection, and non-infection.**

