NOTE: If an HIV-1 resistance genotype is performed as part of clinical care during screening or any time on the study ([section 6.3.2](#)), the site investigator may use this information to guide a change in ART, if clinically indicated, including a change from the study-provided ARV regimen to a non-study-provided ARV regimen or a change from a non-study-provided ARV regimen to the study-provided ARV regimen.

Total HIV-1 DNA

CAHD will be assayed by qPCR in 2 million CD4+T-cells from the **Step 1** entry time point **in participants who have undetectable CAHD at week 48** to ensure that each participant's viral DNA can be amplified by the qPCR assay. This will exclude false negative results for HIV-1 DNA detection at the primary endpoint (week 48) resulting from PCR primer mismatch or other inhibitors of PCR in the participant's sample.

Total HIV-1 DNA will be obtained either from the stored PBMC and plasma or large volume blood collection (or optional leukapheresis).

Primary Endpoint Determination

Please refer to the A5354 LPC for instructions related to the collection, processing, and shipping of these samples.

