10.2 Outcome Measures

10.2.1 Primary Outcome Measures

10.2.1.1 CAHD per 5 million CD4+ T-cells at week 48 **on Step 1**

10.2.2 Secondary Outcome Measures

10.2.2.1 HIV-1-specific CD4+ and CD8+ T-cell responses to nef/tat/rev/vpr/vpu, gag, pol and env by flow cytometry prior to ART initiation and while HIV-1 RNA is suppressed on ART

10.2.2.2 Cell-associated HIV-1 RNA per 5 million CD4+ T-cells prior to ART initiation and while HIV-1 RNA is suppressed on ART

10.2.2.3 Cell-associated HIV-1 RNA/DNA ratio in participants with detectable CAHD prior to ART initiation and while HIV-1 RNA is suppressed on ART

10.2.3 **Other** Outcome Measures

10.2.3.1 Frequency of non-transmitted epitope escape mutants prior to ART initiation and week 48 **on Step 1**

10.2.3.2 CAHD, HIV-1-specific immune responses and single copy HIV-1 RNA in blood; CAHD in gut; and CAHD and single copy HIV-1 RNA in CSF at any time **on Step 1** from week 60 to week 72 in participants who **consent and** undergo the optional procedures and have available data

10.2.3.3 Innate immune responses such as NK cells, ADCC, and ADCP prior to ART initiation and while HIV-1 RNA is suppressed on ART

- 10.2.3.4 Different HIV-1 molecular forms (unintegrated HIV-1 DNA, integrated HIV-1 DNA, total HIV-1 DNA) in participants with detectable CAHD prior to ART initiation and while HIV-1 RNA is suppressed on ART
- 10.2.3.5 Genetic factors such as HLA typing and CCR5 delta-32 genotyping, including relationships with virologic and immunologic outcomes prior to ART initiation and while HIV-1 RNA is suppressed on ART
- 10.2.3.6 Integration sites prior to ART initiation and while HIV-1 RNA is suppressed on ART

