18.2 Cell-associated HIV-1 DNA in participants prior to ART initiation

Pre-ART cell-associated HIV-1 DNA will be summarized using the same approach as week 48 CAHD.

Fold-changes (absolute change in the log₁₀-transformed measurements) from pre-ART measurement in CAHD will be summarized using a similar approach.

Correlations between selected immunology responses (IFNg+ and total response) and week 48 CAHD will be examined using Spearman correlation coefficient (primary analysis population) with and without controlling for the study group.

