19.1 Signs and symptoms of acute retroviral syndrome

Table: summarizing number (%) of participants and the signs and symptoms of acute retroviral syndrome reported in the database, by MedDRA SOC, PT, grade and study group.

19.2 Absolute CD4+ and CD8+ T-cell counts, CD4/CD8 ratio, and HIV-1 RNA prior to and after ART initiation

See section 13.

Other outcome measures from the protocol not listed here will be included in a separate report.

ACTG A5354
Primary Statistical Analysis Plan

[REDACTED]

[REDACTED]

[REDACTED]

[REDACTED]

[REDACTED]	[REDACTED]	[REDACTED]
[REDACTED] [REDACTED] [REDACTED] [REDACTED] [REDACTED]	[REDACTED] [REDACTED] [REDACTED] [REDACTED]	[REDACTED] [REDACTED]
[REDACTED]		[REDACTED]
[REDACTED] [REDACTED]	[REDACTED]	[REDACTED]
[REDACTED]		[REDACTED]
[REDACTED]	[REDACTED]	[REDACTED]
[REDACTED] [REDACTED] [REDACTED]	[REDACTED]	[REDACTED]
[REDACTED]	[REDACTED]	[REDACTED]
[REDACTED] [REDACTED]	[REDACTED]	[REDACTED]
[REDACTED]	[REDACTED]	[REDACTED]
[REDACTED] [REDACTED]	[REDACTED]	[REDACTED]
[REDACTED] [REDACTED]	[REDACTED] [REDACTED]	[REDACTED]
[REDACTED]	[REDACTED]	[REDACTED]
[REDACTED] [REDACTED]	[REDACTED]	[REDACTED]

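### Integrated HIV-1 DNA is to be derived before ART as well as on ART, but the reason given for ignoring unmeasured unintegrated forms covers only samples after 48 weeks, so a pre-ART derived value is an upper bound of unstated error

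*Protocol*

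**What the plan says.** Protocol 1.4.4 sets its scope as "In participants with detectable CAHD at any time point prior to ART initiation and while HIV-1 RNA is suppressed on ART". Within that scope it will "quantify episomal HIV-1 DNA by qPCR for 2-LTR circles" and then "derive the quantity of integrated HIV-1 DNA from the total and unintegrated DNA". A parenthesis deals with the unintegrated forms that are not assayed: "unintegrated linear DNA or 1-LTR circles would have a negligible contribution after 48 weeks of therapy".

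The matching outcome, protocol 10.2.3.4, reads "Different HIV-1 molecular forms (unintegrated HIV-1 DNA, integrated HIV-1 DNA, total HIV-1 DNA) in participants with detectable CAHD prior to ART initiation" and goes on to suppressed on-ART samples. It has no week-48 limit and states no method. The second letter of amendment adds exploratory objectives and outcomes but leaves 1.4.4 and 10.2.3.4 as they are.

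The SAP does not analyse this outcome. Section 19 ends: "Other outcome measures from the protocol not listed here will be included in a separate report". The only change from a pre-ART DNA value that the SAP plans is in 18.2, where fold-changes "from pre-ART measurement in CAHD will be summarized using a similar approach". That concerns total cell-associated HIV-1 DNA (CAHD), not integrated DNA.

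**The concern.** The justification in 1.4.4 is narrower than the use made of it. Linear DNA and 1-LTR circles are not measured, so they stay in the difference and are counted as integrated. The protocol accepts this because it takes them to be negligible after 48 weeks of therapy, and it says nothing about them before ART. Neither document supplies an assay for these forms, a correction, or a label marking the pre-ART value as a bound.

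The study asks how the timing of ART affects establishment of the reservoir. A pre-ART figure reported as integrated DNA could be taken as a measure of reservoir at entry when part of it is unintegrated DNA.

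**Working it through.** The documents give no figure for this point, so there is none to reproduce. The check is a mass balance.

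**Inputs**
- Measured: total DNA T and 2-LTR circles c (protocol 1.4.4).
- Not measured: linear DNA plus 1-LTR circles, h. The protocol takes h as negligible after 48 weeks and gives no pre-ART value. I assume a range of 0% to 90% of T.
- c is not given either. I assume 1% or 5% of T.
- The derivation is read as subtraction. The protocol implies this but does not use the word.

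**Formulas**
- T = I + c + h, where I is true integrated DNA.
- Derived value D = T − c = I + h, so D ≥ I, with equality only when h = 0.
- Overstatement, with T = 1: D/I = (1 − c)/(1 − c − h). As c approaches 0 this becomes 1/(1 − h).

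**Results**

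| Assumed h | c near 0 | c = 1% | c = 5% |
|---|---|---|---|
| 0% | 1.00 | 0.99/0.99 = 1.00 | 0.95/0.95 = 1.00 |
| 10% | 1.11 | 0.99/0.89 = 1.11 | 0.95/0.85 = 1.12 |
| 50% | 2.00 | 0.99/0.49 = 2.02 | 0.95/0.45 = 2.11 |
| 90% | 10.0 | 0.99/0.09 = 11.0 | 0.95/0.05 = 19.0 |

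On the log10 scale with c = 1%, the bias is 0, 0.05, 0.31 and 1.04. The direction follows from the algebra. The size depends wholly on the assumed h.

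**If a change to week 48 were computed.** With h near 0 at week 48, D48 = I48, so log10(D0/D48) = log10(I0/I48) + log10(D0/I0). The apparent fall would be overstated by the same log10 amounts.

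**When the inputs exist.** The Step 1 schedule of evaluations (protocol 6.1) and SAP Table 1 place total HIV-1 DNA by qPCR at entry and week 48, with week 49 if needed. PBMC are stored at weeks 4, 12 and 24, so an earlier on-ART assay is possible from storage, but none is specified. The sample that is scheduled and not covered by the parenthesis is therefore the entry sample.

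**Who has an entry value.** Protocol 6.4.9 describes the entry CAHD assay, in 2 million cells, only "in participants who have undetectable CAHD at week 48", as a check that the participant's viral DNA can be amplified. SAP 18.2 summarises pre-ART CAHD without that restriction. Under 6.4.9 alone, the participants assayed at entry have no detectable week-48 DNA to partition. Under SAP 18.2, entry values would be available more widely.

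**The case against.** The opening clause of 1.4.4 could be read as selecting participants rather than fixing time points. This is possible but unlikely. Objectives 1.4.3, 1.4.5 and 1.4.6 use the same phrase for timing, and on the selection reading 1.4.4 would not say when the forms are measured. It is also true that 10.2.3.4 states no method, so applying the subtraction there is an inference from 1.4.4. It is the natural one, because no other method is described.

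The analysis plan for this outcome is not among the documents, and the separate plan or report may already label or omit pre-ART values. That stands as a limit on what can be concluded. It does not repair the protocol text that such a plan would implement.

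The objection is strongest against readings that go further than the text:
- **That the pre-ART values are wrong.** The documents give no pre-ART share of linear or 1-LTR DNA. At an assumed 10% the overstatement is only 1.11-fold. What they support is an unjustified upper bound.
- **That the fall from pre-ART to week 48 in integrated DNA will be misreported.** No such change is planned. SAP 18.2 covers total CAHD, which needs no subtraction. SAP 19 does say that other outcomes follow the approach used for secondary outcomes, so a change is foreseeable, but it is not specified.
- **That suppressed samples from week 4 onward are affected.** This would need assays of stored cells that neither document schedules.
- **That comparisons between Fiebig groups are biased.** This would need the unmeasured share to differ by stage, on which the documents are silent.

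**Conclusion.** The mismatch holds. As written, integrated DNA is to be derived before ART from assays that cannot separate it from linear and 1-LTR DNA, and the protocol's reason for ignoring those forms applies only after 48 weeks. The pre-ART derived value is an upper bound. Its error is unknown from the documents: about 1.0- to 10-fold over an assumed unmeasured share of 0% to 90% with 2-LTR circles small, and up to 19-fold if 2-LTR circles are 5% of total.

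This rests on reading the derivation as subtraction and the phrase in 1.4.4 as timing. It accepts the protocol's own statement about week 48. The point is minor. It concerns one exploratory outcome and leaves the primary endpoint, total CAHD at week 48, untouched. The secondary outcomes in SAP section 18 do not use derived integrated DNA.

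**What to change.** In 1.4.4, 10.2.3.4 and the separate exploratory analysis plan, state that derived integrated HIV-1 DNA is limited to samples taken at Step 1 week 48 or later. For entry samples, and for any earlier on-ART sample assayed from storage, either report total CAHD and 2-LTR circles as measured, or report the derived value labelled as an upper bound. In either case compute no change from pre-ART in derived integrated DNA.

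In the same edit, reconcile protocol 6.4.9 with SAP 18.2 on which participants have CAHD assayed at entry.

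The cost is about one sentence in each place and no new samples. The small downside is losing a pre-ART derived variable, or keeping it only as a bound. If a pre-ART value of integrated DNA is wanted, it would have to be measured directly in those samples, which would need an additional assay.

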2.0 INTRODUCTION

2.1 Background

Persistent cellular reservoirs of HIV-1 are established very early in AHI [1]. Most proviral DNA is in CD4+ T-cells, particularly central and transitional memory T-cells that persist through homeostatic, antigen-driven, or other mechanisms of proliferation [2]. Very early ART may limit the seeding of cellular reservoirs of HIV-1 [3-5, 6]. Theoretically, ART initiated in the earliest Fiebig stages could limit the size and genetic diversity of the HIV-1 reservoirs, thereby improving the chance of an HIV-1 cure. Paradoxically, however, post-treatment controllers in the VISCONTI cohort were mainly those treated in later Fiebig stages, i.e., IV-V [7]. There are limited data assessing the impact of the timing of ART initiation during AHI on sensitive measures of reservoir size and on virologic and immunologic markers of immune control of HIV-1. Several large studies of early ART in acute and recent HIV-1 infection such as SPARTAC were designed to evaluate clinical outcome and CD4+ T-cells and HIV-1 RNA set point after ART interruption [8]. The RV254 Thai study has enrolled mainly Fiebig I to III AHI participants, which limits its relevance to later Fiebig stages that are more commonly diagnosed in routine patient care. One of the largest studies evaluating residual viremia, proviral DNA and infectious virus after early ART had only 27 participants [4]. Although CHAVI has provided detailed descriptions of the natural history of immunologic events in acute and early HIV-1 infection, their studies did not focus on persons treated with modern ART. A thorough study is thus needed to define the impact of early ART on virologic and immunologic outcomes that are relevant to achieving HIV-1 cure [9]. Current Fiebig staging utilizes HIV-1 RNA, p24 antigen, 3rd generation enzyme immunoassay (EIA, IgM-sensitive), 2nd generation EIA (IgG-sensitive) and Western blot (WB) to categorize AHI into five stages [10].

The duration of these stages varies across individuals and is dependent on the rapidity of the HIV-1-specific antibody response. The protocol team hypothesizes that timing of ART initiation during different stages of AHI will be predictive of the magnitude and characteristics of HIV-1 reservoirs and the quantity and quality of HIV-1-specific immune responses. Longitudinal analysis is needed to evaluate the ability of this staging system to discern the effects of ART instituted in each study group on HIV-1-specific immune responses and HIV reservoirs.

Virologic Outcomes of Interest after Early ART

As noted above, the impact of early ART on the persistence of HIV-1-infected cells has been limited by the number of individuals studied and the detection limits of the assays used to detect persistent HIV-1. Assay detection limits can be improved by sampling larger numbers of cells for HIV-1 nucleic acid. Accordingly, large numbers of CD4+ T-cells (5 million) will be assayed for HIV-1 DNA as the primary study endpoint [11]. Having no HIV-1 DNA in CD4+ T-cells detected by sensitive methods following ART is likely an indication of a limited HIV-1 reservoir that may improve the chance of continued virologic control after ART withdrawal. The timing of ART initiation could affect the number and location of HIV-1 integration sites, which in turn could affect clonal expansion, proviral expression, and responsiveness to anti-latency treatments [12-14].

The impact of ART timing on HIV-1 integration sites could be evaluated utilizing samples collected during this study.

Immunologic Outcomes of Interest after ART

The earliest HIV-1-specific T-cell responses are predominantly oligofunctional with multifunctional response increasing with time after infection. The epitopes recognized by T-cells during AHI may be narrow in range and non-immunodominant. Escape mutations can occur early after infection in some individuals and may impact virologic control [15]. Early ART, depending on the time of its initiation, may prevent the generation of multifunctional T-cell responses [16], but may also preserve HIV-1-specific CD4+ and CD8+ T-cell responses [17-22]. These observations were mainly derived from small studies of patients whose stage of AHI was not well characterized. In addition, the impact of the timing of ART initiation on the frequency of viral immune escape variants is undefined, particularly for minor escape variants that can only be detected by single genome sequencing or next generation sequencing methods. Immune escape variants pose a significant obstacle to immune control of HIV-1; thus identifying the optimal timing of ART initiation to prevent their emergence is an exploratory objective of this study.

To achieve sustained virologic control of HIV-1 (ART-free HIV-1 remission) and to clear virus expressing cells, it is likely that immune-based therapies will be needed in addition to latency-reversing agents, and responses to such therapies may differ depending on the pre-existing immune responses to HIV-1. Thus, the optimal strategy for manipulating the immune system may be different in infected individuals who initiate ART at different Fiebig stages. Defining if and how immune responses persist or evolve over time in infected individuals treated during AHI, and how they relate to reservoir size and viral diversity, will increase our understanding of critical host-viral interactions and inform the development of immune-based therapies for HIV-1 cure.

Tissue HIV-1 Reservoirs

HIV-1 preferentially persists in the gut mucosa, therefore, larger reservoir sizes in gut tissue compared with the peripheral blood are observed even after successful ART [23, 24]. While early ART is more beneficial than later ART in reducing HIV-1 DNA in gut, there are limited data on ART effects on the types of latently infected cells [25-28]. In the central nervous system (CNS), CNS inflammation and CSF viremia are reported within days following HIV-1 exposure [29]. Latently infected cells and inflammation persist in the brain after suppressive ART, but it is not well understood how early ART impacts infected cells, low level virus, inflammation, and neuronal injury in the CSF. Failure to mount an adequate immune response to control viral replication and eliminate HIV-1-infected cells in these compartments could directly jeopardize HIV-1 cure.

The Contribution of A5354 to the Understanding of the Effects of Early ART on HIV-1 Persistence and Immune Responses

The investigators of this study have engaged investigators of other NIH-funded early treatment cohort studies and received enthusiastic response for further cross-study collaborations. All groups aim to identify acutely infected individuals and characterize their HIV-1 reservoir size after treatment. There are important differences between the studies as detailed in [Table 2.1-1](#). Notably, A5354 is unique in its broad inclusion of

individuals across continents who display different genetic profiles and HIV-1 clades, its primary endpoints, and its plans for extended follow-up to facilitate enrollment in interventional trials.

The primary endpoint for A5354 is novel. It is the only study that will extensively interrogate the HIV-1 reservoir after ART by performing tests to identify CAHD in large numbers of CD4+ T-cells. It will secondarily evaluate cell-associated HIV-1 RNA and extensively evaluate the HIV-1-specific immune responses to all HIV proteins, providing important information that will inform strategies for future immune-based therapies. The step-wise approach to performing invasive procedures is innovative and cost-effective. Herein, this study will further investigate persistence of HIV-1 in tissues in those participants whose peripheral blood yields no detectable HIV-1 DNA.

The RV254 Thai cohort establishes and characterizes an AHI cohort in a high risk population. This Division of AIDS (DAIDS)/Department of Defense-funded study commenced in 2009 and as of December 2015 has over 300 participants enrolled. The study is continuing as an open enrolling cohort with an unlimited sample size. The study is conducted at one site in Bangkok with all enrollees being Thai. It has shown so far that HIV-1 reservoir size is small when ART is initiated early. The cohort primarily consists of Fiebig III followed by Fiebig I individuals, limiting the evaluation of outcomes across all Fiebig stages.

The South African cohort, "A Prospective Study of the Virology and Immunology of HIV-1 Infection in South African Blood Donors: Implementation of ART in Very Early HIV-1 Infection and Evolution of Elite Controllers" is a National Heart, Lung, and Blood Institute funded protocol that is being developed as a collaboration between the University of California at San Francisco and the South African National Blood Service (SANBS). The acutely infected individuals will be identified within the SANBS catchment areas and referred for treatment at study sites.

Table 2.1-1. A5354 and Other NIH-funded Early Treatment Cohort Studies

Study	A5354	RV254 Thai Cohort	South African Cohort
Sites	US and international	Single site in Bangkok	5 sites in 4 provinces
Circulating HIV-1 clades	Multiple clades represented	Predominantly CRF01_AE	Predominantly C
Number of participants	196	≥500 with unlimited numbers enrolled	75
Primary objectives	Characterize reservoir/HIV-specific immunity after early ART Cohort of HIV cure research candidates	Characterize reservoir/HIV-specific immunity after early ART Cohort of HIV cure research candidates	Determine Fiebig stages and demonstrate linkage to care for acute HIV-1 infected patients Measure the size of the reservoir after early ART
Fiebig stages	Target 50 for each Fiebig I/II, Fiebig III/IV, Fiebig V	Fiebig I to V (~40% F I/II, 50% F III, 10% F IV/V)	75 Fiebig I/II
Identification of acute HIV-1 infected participants	Performed routinely at the study sites and not part of the protocol	Screening performed as part of the protocol using nucleic acid test (NAT) and sequential EIA	Screening performed as part of the protocol using NAT
Time from enrollment to ART initiation	Same day	Mean 1 day (range 0-7)	4 days to 2 weeks
ART regimens	EVG/COBI/FTC/TAF and BIC/FTC/TAF with some receiving locally available alternatives	TDF/FTC/EFV with some receiving RAL and MVC intensification	TDF/FTC+RAL (week 0-24) TDF/FTC/EFV (week 26-96)
Virologic assessments	CAHD in 5 million CD4+ T-cells (highest sensitivity) as primary endpoint and cell-associated HIV-1 RNA as secondary endpoint	DNA and inducible RNA in small blood volumes except for participants who undergo leukapheresis	DNA and cell-associated RNA in small blood volumes except for participants who undergo leukapheresis

Study	A5354	RV254 Thai Cohort	South African Cohort
Immunologic assessments	Magnitude, distribution, quality of T-cell responses to nef/tat/rev/vpr/vpu, gag, pol and env	Magnitude and breadth of T-cell responses to gag, pol, nef and env and other cellular responses (B, NK) Markers of immune activation	Clinical CD4+ T-cell measurement
Invasive procedures	One time after ART: gut biopsy via flexible sigmoidoscopy and lumbar puncture in a subset of participants after 48 weeks of ART on Step 1	Leukapheresis, gut and lymph node biopsy, lumbar puncture, genital secretion as optional procedures at multiple time points before and after ART	Leukapheresis at 3 time points after ART

Acute HIV-1 Infection Identification

Best effort must be taken to identify and treat persons with AHI. Several strategies may be employed with the goal of being able to enroll participants **across the** study groups (Fiebig I/II, III/IV, or V) which include the following: 1) Frequent routine HIV-1 testing of high risk patients; 2) Outreach to testing sites and clinic/providers administering pre-exposure and post-exposure prophylaxis; 3) Performance of HIV-1 testing within one week of possible HIV-1 exposure and immediately with any acute retroviral syndrome-like symptoms; 4) Engagement of sites that have implemented 4th generation enzyme immunoassay (EIA) or nucleic acid testing as part of HIV-1 testing as well as outreach to testing sites that conduct such tests.

Strategy for Rapid Diagnosis of AHI and Fiebig Staging

Where practical, we recommend deploying routine screening with 4th generation Ag/Ab combo assays (Abbott ARCHITECT HIV-1/2 Combo or Bio-Rad HIV-1/2 Combo or Siemens AVIDA Centaur HIV-1/2 Combo) with preference for the Abbott ARCHITECT chemiluminescence immunoassay (CMIA) because of the rapid test turn-around-time of approximately 30 minutes versus 2 hours for the Bio-Rad; in addition, the broad dynamic CMIA range has the potential to use the S/CO to establish HIV-1 infection recency [30]. Using an algorithm of a 4th generation Ag/Ab assay in combination with emerging technologies for rapid confirmatory and discriminatory HIV-1/2 antibody screening (HIV IgG Multispot or the Geenius assay, once available) [31] followed by rapid HIV-1 RNA testing using either the laboratory-in-a-tube (IQuum/Roche) 30-minute quantitative HIV-1 RNA test or the 60-minute Alere Diagnostics HIV-1/2 RNA assay, it is possible to identify participants in Fiebig I/II on the same day as enrollment.

There are currently four Food and Drug Administration (FDA)-approved 4th generation HIV-1/2 Ag/Ab screening assay platforms that allow for the diagnosis of acute or established HIV-1 infection. All four platforms are able to detect HIV-1 antigen and HIV-1/2 antibodies in blood serum or plasma. One of these platforms is an EIA (Bio-Rad HIV-1/2 Combo Ag/Ab EIA); two are a magnetic microparticle-based CMIA (Abbott ARCHITECT HIV-1/2 Ag/Ab Combo and Siemens ADVIA Centaur HIV-1/2 Ag/Ab Combo assay); and one is a luminex flow-based assay that differentiates HIV-1 antibody from HIV-1 p24 antigen and HIV-1 from HIV-2 antibodies (Bio-Rad BioPlex 2200 HIV Ag-Ab assay). In addition, the recent FDA approval of the confirmatory Bio-Rad Geenius HIV-1/2 lateral flow antibody assay offers an opportunity to replace both the rapid Multispot HIV-1/2 and the WB with a discriminatory rapid (<30 minutes) antibody confirmation of a reactive 4th generation screening test and, in addition, estimates the Fiebig stage based on the detection of HIV-1 gag (p24), pol (p31), and env (gp160, gp41) antibodies and for HIV-2, two env-specific peptides (gp36 and gp140). The available FDA-approved HIV-1 antibody screening and orthogonal confirmatory assays are listed in the A5354 Manual of Procedures (MOPS).

The Centers for Disease Control and Prevention (CDC) 4th generation screening algorithm may be used to identify acute, early, and established HIV-1 infection (see A5354 MOPS). Where available the Geenius assay will be done immediately on site to detect or confirm HIV-1 antibody and to allow a preliminary Fiebig staging. Where

appropriate (e.g., reactive screen and negative antibody assay (e.g., Multispot or Geenius), an HIV-1 RNA will be performed at the site.

An analysis of 39,721 specimens tested from a combined research and clinical testing service showed that the ARCHITECT S/CO clearly distinguished the false positive (0.2%) from AHI (0.1%) and established infection (1.33%) (Figure 2.1-1). Interestingly, 0.7% of the specimens had a S/CO of between 0.50 and 0.99. Three (10%) of the 30 AHI had a S/CO of between 0.50 and 0.99, which suggests that in a high-seroincidence population, a S/CO less than 1.0 may identify additional AHI [30, 31].

We posit that the strength of the S/CO will equate with the likelihood of a particular infection stage in this high seroincidence study population.

[figure not shown]

Figure 2.1-1. Distribution of ARCHITECT S/CO values: A, B: non-reactive; C: intermediately reactive; D: false-positive; E: acute HIV-1 infection; F: established infection [32]

We have shown that the 4th generation ARCHITECT HIV-1/2 Ag/Ab Combo assay in comparison to the 4th generation Bio-Rad Combo provides a greater dynamic S/CO range for determining recent infection (Figure 2.1-2). The ARCHITECT S/CO was also shown to be useful for differentiating acute from recent and established HIV-1 infections

based on an indeterminate or confirmed WB with or without the presence of HIV-1 p31 antibody (Figure 2.1-3). However, in conjunction with the Geenius assay, the Fiebig classification can be estimated as I-II (RNA or p24 antigen positive [or both] and no antibody) versus III-IV (IgM/IgG with negative or indeterminate WB) versus V (confirmed WB and no anti-p31) versus VI (confirmed WB and anti-p31).

[figure not shown]

Figure 2.1-2. ARCHITECT versus GSCOMBO for S/CO values over the range of HIV-1 infection [32]

[figure not shown]

Figure 2.1-3. ARCHITECT S/CO for HIV-1 infection recency [32]

For the purpose of this study, a S/CO ratio ≥ 10 is considered “positive” in the ARCHITECT assay. However, a S/CO of between 0.5 and 10 that corresponds to HIV-1 p24 antigen positive AHI represents between 4-5.5 \log_{10} HIV-1 RNA copies/mL [30]. Therefore, HIV-1 p24 antigen detection at a S/CO of 0.5 may correspond to approximately 6,000 HIV-1 RNA copies/mL (Figure 2.1-4 below), which is well above the lower limit of assay detection for commercial assays. Participants with a previous ARCHITECT S/CO ratio of < 0.5 who now have a value ≥ 1.0 are eligible to enroll in the study pending the HIV-1 RNA determination. Potential participants with S/CO > 0.5 but < 10 will require a positive HIV-1 RNA results prior to enrollment (this criterion will decrease the incidence of false-positive HIV-1 infection).

[figure not shown]

Figure 2.1-4. The log₁₀ linear relationship between the HIV-1 RNA copies/mL of plasma (abscissa) and the ARCHITECT assay S/CO values (ordinate)

Challenges

The majority (19/23, 83%) of the ACTG international laboratories have an Abbott m2000 system available, 10/23 (43%) also have the Roche COBAS TM, and most of the laboratories conduct HIV-1 RNA testing on-site. However, the turn-around-times (TAT) for results is highly variable from <24 hours up to 14 days even for on-site testing. The average TAT is 4.6 days and the median is 3 days. These times are independent of instrument; i.e., if it takes 2 days for results at one laboratory on the Roche COBAS TM, it also takes 2 days for results at the same laboratory using the Abbott m2000 system. Inclusion criteria for this study are designed to identify individuals during AHI while accommodating differences in testing at various study sites. Fiebig staging will be performed using standardized processes at reference laboratories on samples collected on the day of study entry.

PCR Assay for Detection of CAHD and Cell-associated RNA in CD4+ T-cells

A qPCR assay with single-copy sensitivity targeting a highly conserved region of integrase in the HIV-1 *pol* gene [33] will be used to detect HIV-1 DNA or RNA in 5 million total CD4+ T-cells.

Antiretroviral Regimen

The study will provide the open-label EVG/COBI/FTC/TAF **or BIC/FTC/TAF** to all enrolled participants. The availability of **these** single-tablet regimen (STR) integrase strand transfer inhibitor (INSTI)-based regimens will facilitate the rapid initiation of therapy and reduction in viral load for those identified with AHI. Single-tablet regimens may demonstrate improved adherence and participant satisfaction over multi-pill regimens, and INSTI-containing regimens have repeatedly been shown to result in more rapid reduction in viral load when compared with non-INSTI-based therapy [34, 35]. EVG/COBI/FTC/TAF **and BIC/FTC/TAF** have been approved by the US FDA **and both include** the TAF formulation of tenofovir, which appears to have distinct safety advantages **over TDF**.

TAF is a second generation oral prodrug of tenofovir, a nucleotide analog that when phosphorylated inhibits HIV-1 reverse transcriptase. TAF is metabolized to tenofovir intracellularly and can be used at a fraction of the dose of TDF with lower blood levels and higher intracellular levels. [36] There have been many clinical trials that have included TAF as well as EVG/COBI/FTC/TAF, including a phase II study (GS-US-292-0102) that included 58 participants treated with the regimen with 88.4% having HIV-1 RNA <50 copies/mL at 48 weeks by snapshot analysis compared with 87.9% in those given EVG/COBI/FTC/TDF. Results from the pharmacokinetic study showed that 10 mg TAF resulted in lower blood plasma levels of tenofovir than TDF at 300 mg with approximately five-fold higher levels of tenofovir diphosphate in peripheral blood mononuclear cells (PBMC) than with TDF.

Two phase III registrational trials (GS 104 and GS 111) have been completed and published comparing EVG/COBI/FTC/TDF with EVG/COBI/FTC/TAF in a combined study of more than 1700 ART-naïve individuals [37]. It is noteworthy that although the median CrCl of enrolled participants exceeded 100 mL/minute, the studies did allow for enrollment of participants with CrCl \geq 50 mL/minute. The proportion with plasma HIV-1 RNA <50 copies/mL through 48 weeks by snapshot analysis was 90% in the TDF- versus 92% in the TAF-containing regimens with adjusted difference of 2.0%, 95% CI - 0.7 to 4.7, meeting pre-specified non-inferiority criteria. Furthermore, there was no difference in response in either group based upon baseline plasma HIV-1 RNA (less than or equal to or greater than 100,000 copies/mL) or CD4+ T-cell count (less than or greater than or equal to 200 cells/ μ L). Protocol-specified virologic failure (VF) was similar and low in both groups as was emergent drug resistance, and the pattern of such resistance was similar between study groups. The mean increase in CD4+ T-cell count was significantly greater at 48 weeks in the TAF versus TDF group at 230 versus 211 cells/ μ L, respectively ($p=0.024$). The frequency of any AE was 90% in both groups with only 1% in each group having drug-related Grade 3 or 4 AEs. Common AEs occurring at least in 5% of individuals were also similar between groups with most frequent being diarrhea, nausea, and headache. Special attention was given to the difference in effect

on renal **function** and bone **density** in these studies since these are recognized AEs associated with TDF use. The TAF group had significantly smaller mean serum creatinine increases than those given a TDF-based regimen (0.08 versus 0.12 mg/dL, $p < 0.001$), less proteinuria (median percent change -3.0 versus 20; $p < 0.001$), and significantly smaller decrease in bone mineral density at spine (mean % change -1.3 versus -2.86; $p < 0.001$) and hip (mean % change -0.66 versus -2.95; $p < 0.001$). There was a significantly greater increase in total, LDL and HDL cholesterol as well as triglycerides in those receiving a TAF- rather than a TDF-containing regimen, although no difference was seen in total cholesterol:HDL ratio. The package insert for EVG/COBI/FTC/TAF allows for treatment of participants with CrCl ≥ 30 mL/minute **GENVOYA [package insert]. Gilead Sciences, Inc., Foster City, CA; March 2016. http://www.gilead.com/~/media/files/pdfs/medicines/hiv/genvoya/genvoya_pi.pdf. Accessed Mar 30, 2016**. Participants with CrCl < 30 mL/minute can be included in the study if they are able to access appropriate alternate regimens according to local guidelines.

